f. Not relevant to me.	f

Section C:

1

Which of the following symptoms apply to you at this time? Please, mark the appropriate box for each symptom. For symptoms that do not apply, please mark 'none'.

Symptoms:

	none	mild	moderate	severe	very severe
Score	0	1	2	3	4
1. Hot flushes, sweating (episodes of sweating)					
2. Heart discomfort (unusual awareness of heart beat, heart skipping, heart racing, tightness)					
3. Sleep problems (difficulty in falling asleep, difficulty in sleeping through, waking up early)					
4. Depressive mood (feeling down, sad, on the verge of tears, lack of drive, mood swings)					
5. Irritability (feeling nervous, inner tension, feeling aggressive)					
6. Anxiety (inner restlessness, feeling panicky)					
7. Physical and mental exhaustion (general decrease in performance, impaired memory, decrease in concentration, forgetfulness)					
8. Sexual problems (change in sexual desire, in sexual activity and satisfaction)					
9. Bladder problems (difficulty in urinating, increased need to urinate, bladder incontinence)					
10. Dryness of vagina (sensation of dryness or burning in the vagina, difficulty with sexual intercourse)					
11. Joint and muscular discomfort (pain in the joints, rheumatoid complaints)					

Have you ever used hormone replacement therapy (HRT)? (tick one below)

[figure not shown]
a. Yes I am using it currently.	a
b. Yes I have used it in the past but not at the moment.	b
c. No.	c
d. I don't know what hormone replacement therapy (HRT) is.	d

2 If you have ever had any of the symptoms above, and thought that these might be due to the menopause, is there anything else you did to relieve your symptoms?

Please write below:

Finished!
Well done

Thank you for answering all these questions.
Your answers are very important to the study

Visit 3 Respiratory Questionnaire

STUDY NUMBER:

PATIENT INITIALS:

DATE OF COMPLETION:

FOR RESEARCH STAFF:

Complete details above.

Ensure that all participants complete questions 1-6 and, if any symptoms are reported (indicated by an *), that they also complete the rest of the questionnaire.

FOR STUDY PARTICIPANT:

This questionnaire is designed to help us learn how your breathing may or may not be troubling you, and how your breathing may or may not affect your life.

We ask everyone to complete the first 6 questions.

We then only ask you to complete the rest of the questionnaire (questions 7 to 40) if you report some form of breathing difficulties in your answers to the first 6 questions.

Please read the instructions carefully and ask if you do **not** understand something. Do not spend too long deciding about your answers.

The following questions are about how much trouble you have with your breathing.

Please mark one box for each question:

1. I cough:

- 1 Most days of the week*
- 2 Several days of the week*
- 3 Only with chest infections
- 4 Not at all

2. I cough up phlegm (sputum):

- 1 Most days of the week*
- 2 Several days of the week*
- 3 Only with chest infections
- 4 Not at all

3. I am short of breath:

- 1 Most days of the week*
- 2 Several days of the week*
- 3 Not at all

4. I have episodes or attacks of wheezing:

- 1 Most days of the week*
- 2 Several days of the week*
- 3 A few days a month*
- 4 Only with respiratory infections
- 5 Not at all

5. How many sudden shortness of breathing episodes did you have during the last year?

- 1 3 or more episodes*
- 2 1 or 2 episodes *
- 3 None

6. How often do you have good days (with few chest or breathing problems)?

- 1 No good days*
- 2 A few good days*
- 3 Most days are good
- 4 Every day is good

*If any answer with an *asterisk* has been selected, please complete the rest of the questionnaire. If you have not ticked any of the answers with an asterisk, please do not proceed. This is the end of the questionnaire.

Please mark one box for each question:

7. If you wheeze, is it worse when you get up in the morning?

- 1 No
- 2 Yes
- 3 Don't wheeze

8. How would you describe your chest problem(s)?

- 1 Cause me a lot of problems or are the most important physical problems I have
- 2 Cause me few problems
- 3 Cause no problems

For each of the following activities, please state whether the activity makes you feel breathless or not.

For each statement please mark the box that applies to you these days

	Yes	No
9. Washing or dressing yourself	 1	 2
10. Walking around the house	 1	 2
11. Walking outside on level ground	 1	 2
12. Walking up a flight of stairs	 1	 2
13. Walking up hills	 1	 2

Please say whether each of the statements applies to you or not.

For each statement please mark the box that applies to you these days

	Yes	No
14. Coughing hurts	 1	 2
15. Coughing makes me tired	 1	 2
16. I am short of breath when I talk	 1	 2
17. I am short of breath when I bend over	 1	 2
18. My coughing or breathing disturbs my sleep	 1	 2
19. I get exhausted easily	 1	 2

Please say whether each of the statements applies to you or not.

For each statement please mark the box that applies to you these days

	Yes	No
20. My cough or breathing is embarrassing in public	 1	 2
21. My chest problems are a nuisance to my family, friends or neighbours	 1	 2
22. I get afraid or panic when I cannot catch my breath	 1	 2
23. I feel that I am not in control of my chest problems	 1	 2
24. I have become frail or an invalid because of my chest problems	 1	 2
25. Exercise is not safe for me	 1	 2
26. Everything seems too much of an effort	 1	 2

Statements about how your activities might be affected by your chest problems.

For each statement please mark the box that applies to you these days

	True	False
27. I take a long time to get washed or dressed	 1	 2
28. I cannot take a bath or shower, or I take a long time to do it	 1	 2
29. I walk slower than other people my age, or I stop to rest	 1	 2
30. Jobs such as household chores take a long time, or I have to stop to rest	 1	 2
31. If I walk up one flight of stairs, I have to go slowly or stop	 1	 2
32. If I hurry or walk fast, I have to stop or slow down	 1	 2
33. My breathing makes it difficult to do things such as walk up hills, carry things up stairs, light gardening such as weeding, dance, bowl or play golf	 1	 2
34. My breathing makes it difficult to do things such as carry heavy loads, dig in the garden or shovel snow, jog or walk briskly (5 miles per hour or 8km/h), play tennis or swim	 1	 2

Statements about how your chest problems usually affect your daily life.

For each statement please mark the box that applies to you these days

	True	False
35. I cannot play sports or do other physical activities	 1	 2
36. I cannot go out for entertainment or recreation	 1	 2
37. I cannot go out of the house to do the shopping	 1	 2
38. I cannot do household chores	 1	 2
39. I cannot move far from my bed or chair	 1	 2

40. How do your chest problems affect you (please mark one box)?

- 1 They do not stop me from doing anything I would like to do
- 2 They stop me from doing one or two things I would like to do
- 3 They stop me from doing most of the things I would like to do
- 4 They stop me from doing everything I would like to do

Thank you for filling out this questionnaire

Before you finish would you please check to see that you have answered all the questions.

This form is based on a questionnaire developed by P.W. Jones, Ph.D., F.R.C.P., St George's University of London, London, United Kingdom. Copyright reserved.

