6.0 Study Specific Procedures

6.1 DEXA scanning

All study subjects will undergo a regional (hip and spine) and whole body DXA scan where available (only if urinary β hcg is negative in female subjects under the age of 50). Total and regional bone mineral density Z and T scores will be estimated and total and regional fat and lean mass calculated. All scans will be performed by medical staff and reported by a consultant radiologist and should be performed within 30 days of the clinic visit.

The reports of the scans will be sent to the patients GPs where permission for contact is in place. In the cases where no permission is granted for GP contact, the results will be sent to the health care professional in charge of that patient within the clinic. In all cases any abnormalities detected will therefore be actioned.

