7.0 Study Management

Imperial College London will act as the nominated sponsor for this study. All project documentation will be submitted to the sponsor for approval prior to submission to regulatory bodies such as a Research Ethics Committee (REC).

The study will comply with the requirements of The Research Governance Framework (2nd Edition) and the ethical principles described in the current revision of the Declaration of Helsinki. The study will also be carried out in keeping with local legal and regulatory requirements.

Before the first subject is enrolled into the study all ethical and legal requirements must be met and ethics and R&D approval should have been obtained.

The REC and R&D offices and sponsor will be informed of all subsequent protocol amendments. Amendments will be evaluated to determine whether or not they are substantial and therefore if formal approval must be sought and whether the informed consent documents should also be revised.

The study will be coordinated from the Imperial Clinical Trials Unit (ICTU), which holds provisional registration as a UKCRC Trials Unit. An experienced study co-ordinator, based in the ICTU and working under the supervision of [name], will manage the day-to-day running of the study. Statistical support will be provided by a statistician working at UCL under the supervision of [name].

This study will not open to recruitment until appropriate approvals and authorisations have been obtained from an independent ethical committee. Recruitment will not commence at an individual participating site until local NHS Management approval has been obtained and all local documentation is in place and all requirements have been fulfilled according to ICTU Standard Operating Procedures (SOPs).

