'We would like to know how much of your HIV medication you have taken recently. We understand that many people on HIV medication find it very difficult to take it regularly and often miss doses so we won't be surprised if you have missed lots of doses as well. We need to know how many doses you have missed.'

This questionnaire is completely confidential. Under no circumstance will your answers be shown to your doctor or anyone else involved with your care.'

QA How many doses of HIV medication did you miss yesterday?

- 0
- 1
- 2

- 3
- Don't know

QB How many doses of HIV medication did you miss the day before yesterday?

- 0
- 1
- 2

- 3
- Don't know

QC How many doses of HIV medication did you miss the day before that? (3 days ago)

- 0
- 1
- 2

- 3
- Don't know

QD How many doses of HIV medication have you missed in the last 2 weeks?

- 0
- 1
- 2
- 3-5
- 6-10

- 11-20
- 20-40
- More than 40
- All of them
- Don't know

QE Put a cross on the line below at the point showing your best guess about how much HIV medication you have taken in the last month. We would be surprised if this was 100% for most people.

e.g. 0% means you have taken no HIV medication

50% means you have taken half your HIV medication

100% means you have taken every single dose of your HIV medication

QF When was the last time you missed a dose of HIV medication ?

- Today
- Yesterday
- Earlier this week
- Last week

- Less than a month ago
- More than a month ago
- Never
- Don't know

STUDY NUMBER:
PATIENT INITIALS:
DATE:
VISIT:

Questionnaire

Thank you for taking the time to fill in this questionnaire.

If you would like help with filling in the questionnaire, one of the study team will be happy to help you.

All information that you give will be treated as strictly confidential.

The nursing team will not assess your answers, they will be entered anonymously at Imperial College.

Take your time – it is not a competition.

Your answers are very important to the POPPY study.

They will give us a good idea how we may treat people as they get older.

The questions will take about 30 minutes to answer.

INSTRUCTIONS

Fill out your answers with a black pen provided – put a cross in the box which most fits your response. The boxes vary in size.

COGNITIVE COMPLAINTS		Never	Hardly ever	Yes, definitely
Q1	Do you experience frequent memory loss (for example, do you forget the occurrence of special events even the more recent ones, appointments etc.)?			

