Q53	I felt lonely				
Q54	People were unfriendly				
Q55	I enjoyed life				
Q56	I had crying spells				
Q56a	I felt sad				
Q57	I felt that people dislike me				
Q58	I could not get "going"				

Over the last 2 weeks, how often have you been bothered by

		Not at all	Several days	More than half the days	Nearly every day
Q59	Little interest or pleasure in doing things				
Q60	Feeling down, depressed or hopeless				
Q61	Trouble falling asleep, staying asleep, or sleeping too much				
Q62	Feeling tired or having little energy				
Q63	Poor appetite or overeating				
Q64	Feeling bad about yourself – or that you're a failure or have let yourself or your family down				
Q65	Trouble concentrating on things, such as reading the newspaper or watching television				
Q66	Moving or speaking so slowly that other people could have noticed. Or the opposite – being so fidgety or restless that you have been moving around a lot more than usual				
Q67	Thoughts that you would be better off dead, or of hurting yourself.				

RISK OF FALLING:

Q68	Over the past 28 days have you had any falls?	I have not fallen	Once	Twice	Three or more times

If you have had no falls please do not answer the next few questions and proceed to question 73, otherwise please answer the next question.

Where have you fallen?

Q69	Inside You may tick more than one	On the one level	
		Getting out of bed	
		Getting out of a chair	
		Using the shower/bath	
		Using the toilet	
		Walking up or down stairs	
		Other	
	Home entrance or in the garden You may tick more than one	Walking up or down a step	
		On the one level (e.g path)	
		In the garden	
		Other	
	Away from home: You may tick more than one	On the footpath	
		On a kerb/gutter	
		In a public building	
		Getting out of a vehicle	
		In another person's home	
		Other	

Q70	How did you fall? Tick more than one if necessary							
	I tripped	I slipped	I lost my balance	My legs gave way	I felt faint	I felt giddy/dizzy	I am not sure	Other
Q71	As a result of this fall or falls did you suffer any injuries?				Yes	No		

Q72 If yes, what type of injuries did you suffer?						
Bruises	Cuts/grazes	Broken wrist	Broken hip	Broken ribs	Back pain	Other

--	--	--	--	--	--	--

[figure not shown]
[figure not shown]
[figure not shown]
ACHES AND PAINS

Q73	During the past month have you had any aches or pains which have lasted for one day or longer?	Yes	No

if YES, please continue with question 74, otherwise go to question 78

		Yes	No

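### The questionnaire asks about recent thoughts of self-harm (Q67) under a cover page saying nurses will not assess answers, and the visible plan gives no step for a positive answer

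*Combined protocol and SAP*

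**What the plan says.** Appendix 1 holds the participant questionnaire. Items Q59 to Q67 share a two-week recall period and four frequency answers, from 'Not at all' to 'Nearly every day'. The last of them, Q67, reads "Thoughts that you would be better off dead, or of hurting yourself".

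The cover page makes three statements that bear on it:

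- On confidentiality: "All information that you give will be treated as strictly confidential". No exception is stated.
- On who reads the answers: "The nursing team will not assess your answers, they will be entered anonymously at Imperial College".
- On assistance: "If you would like help with filling in the questionnaire, one of the study team will be happy to help you".

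The form's header has fields for the study number and "PATIENT INITIALS", with the date and visit. The main questionnaire closes with thanks and gives no pointer to sources of help.

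Elsewhere, section 6.1 sets a route for bone scan findings. Reports go to the GP where contact is permitted, and otherwise to the clinic professional responsible for the patient. It concludes: "In all cases any abnormalities detected will therefore be actioned".

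**The concern.** A two-week recall period makes Q67 a question about current or recent risk. The participant answers it at a study visit, where someone could respond. The cover page, however, says that the staff running the visit will not assess the answers, and the visible plan names nobody else who will do so in time to act.

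At stake is participant safety. A person may disclose thoughts of self-harm on a form that carries identifying details, and leave without anyone at the site knowing. The form also shapes what participants expect. Some may assume that somebody will respond; others may rely on the promise that the site will not read the answer. The wording should match whatever is actually done.

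**Working it through.** No arithmetic applies, and the plan states no figure on this point to reproduce. The check was to read all the visible text for a review, alert, escalation or referral step that would reach a positive Q67, and to set each candidate beside the cover page.

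1. **Cover page, Appendix 1.** It directs the answers away from the nursing team to central entry, and states no exception for risk of harm. Despite the word 'anonymously', the study number and initials mean that an answer can be linked to a participant, so escalation is feasible.

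2. **Help with completion, Appendix 1.** A team member who helps may see Q67. The help is optional, and nothing visible says what that person should do with a positive answer.

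3. **Section 6.1, bone scans.** This is a real duty to act, with a usable GP-or-clinic route, but it covers scan abnormalities only.

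4. **Sections 7.1 and 7.1.2, adverse events.** These cover events seen by the investigator or reported by the subject, record remedial action, and require follow-up until symptoms subside. This is a visible duty to act on what a participant reports. It does not mention questionnaire answers, however, and a tick on a form that nurses are said not to assess may not reach the investigator. The seriousness criteria do not list thoughts of self-harm.

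5. **Sections 5.3 and 5.4, Visits 2 and 3.** Participants are asked about past-year use of services, including psychiatrists and psychologists. That records contact with care, not present thoughts.

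6. **GP contact, sections 4.1, 5.3, 5.4 and 6.1.** Permission for GP contact is an entry criterion for the HIV-negative cohort. Elsewhere, permission is sought for details of health-care use, or contact is used for scan reports. A channel exists, but Q67 does not trigger it.

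7. **Respiratory questionnaire, Appendix 1.** Its staff instruction begins "Ensure that all participants complete questions 1-6 and, if any symptoms are reported". Its purpose is complete data, since reported symptoms lead to the remaining questions. It shows that asking staff to look at particular answers is workable on a form of this kind, but it is not a safety step.

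None of the seven supplies a reviewer, threshold, time limit or referral for Q67.

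**The case against.** The strongest reply is that this is an absence, and the likeliest places for a safeguard cannot be seen. The consent pages, where limits to confidentiality would normally be explained, were removed. Section 7.0 ties site opening to the trials unit's SOPs, and sections 7.2 and 7.3 call for a risk assessment and a monitoring plan. None of these is in the file. This objection stands. A reader might infer that the study has no safeguard for Q67, but the documents do not support that.

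A reader might also infer that any unseen procedure must contradict the cover page. That goes too far. The sentence concerns the nursing team only. Review by a site doctor, or an alert raised at central data entry using the study number, would not literally contradict it. The separate confidentiality line could still be at odds with passing the answer on, depending on what the consent pages say.

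A third tempting step is to cite the promise that answers will never be shown to the participant's doctor. That promise belongs to the separate adherence questionnaire and says nothing about Q67.

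It can also be said that 'assess' may mean only 'score', and that usual care continues throughout. Neither closes the gap. No visible step asks anyone to look at Q67, and none tells the usual clinicians what was answered.

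**Conclusion.** The point holds for the visible documents. The form asks about recent thoughts of self-harm, tells participants that nurses will not assess the answers, and is accompanied by no visible review or referral step. This is more than missing detail, because the stated rule itself works against a positive answer being noticed at the visit.

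The conclusion assumes that the form is used as printed and that no unseen procedure covers Q67. If one exists, the remaining question is narrower: does the cover wording agree with it? Conflict would arise only if the procedure used nurse review or went beyond the confidentiality stated.

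The documents give no expected frequency of positive answers, so the number of participants concerned cannot be estimated. Sample size, power and the planned analyses are untouched. This is an inexpensive improvement that should be made, held with medium confidence because of what cannot be seen.

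**What to change.** First establish whether a Q67 procedure already exists in the consent documents or SOPs. If it does, align the cover wording with it. If it does not:

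- **Reword the two cover sentences** on confidentiality and on the nursing team so that they make an exception for Q67. For example: *Your answers are confidential and are entered under your study number. The one exception is question 67: a member of the site study team will look at that answer before you leave and may talk to you about it.*
- **Add a 'For research staff' line**: check Q67 before the participant leaves, and pass any answer other than 'Not at all' to the site investigator. The investigator then uses the GP-or-clinic route that section 6.1 already describes for scans.
- **Apply the change to forms completed after approval.** Earlier forms were completed under the existing promise.
- **Leave the adherence questionnaire's own promise as it is.**

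The main cost is a protocol amendment. Section 7.0 says "Amendments will be evaluated to determine whether or not they are substantial and therefore if formal approval must be sought", and also asks whether consent documents need revision. A change to a confidentiality statement may require both. The other costs are a one-item check by existing staff on each later form and possibly less candour on Q67.
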